9.1.2 Packaging

In the Double-blind Treatment Phase HP-5000 [REDACTED] HP-5000 [REDACTED] and placebo patches will be packaged so as to be blinded to the investigator, the study clinic personnel, and the subjects.

Sites and subjects will be instructed to save all empty packaging or packaging containing unused patches for final disposition by the sponsor or its designee.

The Drug Dispensing Log must be available for monitoring, auditing, or inspection. **Section 9.8** details the accountability of clinical supplies through the use of a Drug Dispensing Log.

9.2. Treatments Administered

HP-5000 will be administered [REDACTED] for a maximum of 28 ± 2 days.

The treatment arms for this study are the following:

Treatment Arm	Treatment
HP-5000 [REDACTED]	One patch applied [REDACTED] to alternate side of the target knee (inner or outer).
HP-5000 [REDACTED]	One patch applied [REDACTED] to alternate side of the target knee (inner or outer).
Placebo	One patch applied [REDACTED] to alternate side of the target knee (inner or outer).

Patch Application

A separate guidance for patch application will be provided to subjects for applying, securing, and removing the patch.

9.3. Dispensing and Storage

Study drug supplied by [REDACTED] is to be used exclusively in the clinical study according to the instructions of this protocol. The investigator is responsible for dispensing study drug according to the dosage scheme and for ensuring proper storage of study drug.

The investigator must confirm the receipt of study drug with his/her signature. A copy of this receipt must be kept by the investigator, and another copy will be stored at Noven Pharmaceuticals, Inc. (hereafter referred to as "Noven"), and/or [REDACTED] Until study drug is dispensed to the subjects, it must be stored at 25°C and in a dry place in a securely locked area that is not generally accessible.

All study drug supplies must be stored in a secure locked area with access limited to the investigator or those persons authorized by the investigator to dispense the study drug to subjects. Study drug should be stored as per the label.

9.4. Method of Assigning Subjects to Treatment Groups

In this parallel-group randomized study, subjects who will meet study entry criteria will be randomly assigned in a 1:1:2 ratios to receive HP-5000 [REDACTED] HP-5000 [REDACTED] or placebo patches, respectively. The randomization numbers will be assigned sequentially through a

central interactive voice response system (IVRS) as subjects who met eligibility criteria are enrolled into the study. The study center will not be a blocking factor in the randomization schedule. At designated visits, subjects will be given a kit containing sufficient study drug to last until the next scheduled study visit.

The randomization schedule will be prepared by [REDACTED] before the start of the study. No one involved in the clinical conduct will have access to the randomization schedule before official unblinding of treatment assignment. No subject will be randomized into this study more than once.

9.5. Blinding and Unblinding Treatment Assignment

To protect the blind, placebo patches will be identical in appearance to the HP-5000 [REDACTED] and HP-5000-[REDACTED] patches.

All subjects, investigators, and study personnel involved in the conduct of the study, including data management, will be blinded to study drug treatment assignment with the exception of a prespecified unblinded statistician/programmer from [REDACTED] who will have access to the randomization code. The unblinded study personnel will not participate in study procedures or data analysis prior to unblinding of the study data to all study related personnel. If an interim analysis is to be conducted, then unblinded personnel who are not otherwise involved in the study will prepare the data for review.

Study personnel will endeavor to safeguard the integrity of the study blind to minimize bias in the conduct of the clinical study. Treatment unblinding is discouraged if knowledge of the treatment assignment will not materially change the planned management of a medical emergency. Unblinding will be permitted in a medical emergency that requires immediate knowledge of the subject's treatment assignment.

In the case of a medical emergency, to appropriately treat the subject, study drug will need to be unblinded. The investigator may break the randomization code for an individual subject. However, the investigator should make every effort to discuss the unblinding of the subject with the medical monitor prior to unblinding whenever possible.

If the investigator is not able to discuss treatment unblinding in advance, then he/she must notify the medical monitor immediately of the blind breaking incident without revealing the subject's treatment assignment.

In all such cases, the AE necessitating the emergency blind break will be handled as an SAE in accordance with the procedures indicated above. Any broken code will be clearly justified, explained by a comment on the appropriate eCRF page along with the date and reason for study discontinuation; and captured on the SAE Form.

The investigator or designee must record the date and reason for unblinding or study discontinuation on the appropriate eCRF for that subject. In all cases that are not emergencies, the investigator must discuss the event with the medical monitor prior to unblinding the subject's treatment assignment.

If treatment assignment is unblinded for an individual subject, study personnel will be notified of that subject's treatment assignment without unblinding the treatment assignments for the remaining subjects in the study. Thus, the overall study blind will not be compromised. If a subject's treatment assignment is unblinded, he/she may or may not be asked to withdraw from the study. The investigator will make this decision after consultation with the medical monitor.

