10.2.2.4 Evaluations of Patch and Dermal Assessment

Patch Adhesion

Patch adhesion will be assessed in two ways (in-clinic and at-home). At each clinic visit, patch adhesion will be assessed by the investigator or a designee using the following 5-point numerical scale:

- 0 = $\geq 90\%$ adhered (essentially no lift off the skin).
- 1 = $\geq 75\%$ to $< 90\%$ adhered (some edges only lifting off of the skin).
- 2 = $\geq 50\%$ to $< 75\%$ adhered (less than half of the system lifting off of the skin).
- 3 = $< 50\%$ adhered but not detached (more than half the system lifting off of the skin without falling off).
- 4 = patch detached (patch completely off the skin).

During the Double-blind Treatment Phase at home, subjects will only report on any incidence of patch detachment in the eDiary.

Irritation

At each clinic visit, the application site where the previous patch was applied will be examined for signs of skin irritation. All subjects will be evaluated by a trained investigator or designee using the Berger and Bowman scale (Berger and Bowman 1982) as described below.

Half grades will not be assigned if reactions fall between the unit grades, rather, the more severe of the 2 grades will be assigned.

Dermal Response

- 0 = no evidence of irritation
- 1 = minimal erythema, barely perceptible
- 2 = definite erythema, readily visible; minimal edema or minimal papular response
- 3 = erythema and papules
- 4 = definite edema
- 5 = erythema, edema, and papules
- 6 = vesicular eruption
- 7 = strong reaction spreading beyond the application site

Other Effects

- A = slightly glazed appearance
- B = marked glazed appearance

- C = glazing with peeling and cracking
- F = glazing with fissures
- G = film of dried serous exudates covering all or part of the patch site
- H = small petechial erosions and/or scabs
- N = no other observations

Dermal response score will be rated on a 0 to 7 scale, whereby 0 is rated as “No evidence of irritation” and 7 is rated as “Strong reaction spreading beyond test (application) site.”

Other effects will be scored via a letter scale and a corresponding numeric scale, whereby N (0) is rated as “No effects” and H (3) is rated as “Small petechial erosions and/or scabs.”

During the Double-blind Treatment Phase at home, subjects will complete a questionnaire about skin irritation in the eDiary.

Discomfort

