11.2.2.5 Adverse Event Relationship to Investigational Product

The investigator must make an assessment of each AE's relationship to study drug. The categories for classifying the investigator's opinion of the relationship are listed below.

Not related	An AE with sufficient evidence to accept that there is no causal relationship to study drug administration (e.g., no temporal relationship to drug administration, because the drug was administered after onset of event; investigation shows that the drug was not administered; another cause was proven).
Unlikely related	An AE, including laboratory test abnormality, with a temporal relationship to study drug administration that makes a causal relationship improbable, and in which other drugs, events or underlying disease provide plausible explanations.
Possibly related	An AE with a reasonable time sequence to administration of the study drug, but which could also be explained by concurrent disease or other drugs or events. Information on drug withdrawal may be lacking or unclear.
Definitely Related	An AE occurring in a plausible time relationship to study drug administration, and which cannot be explained by a concurrent disease or other drugs or events. The response to withdrawal of the drug (dechallenge) is clinically reasonable.

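### Protocol 9.5 tells study personnel an unblinded subject's treatment with no need-to-know limit, although the same section requires those personnel to stay blinded and lets the subject remain in the trial

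*Protocol*

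**What the plan says.** Protocol 9.5 (Blinding and Unblinding Treatment Assignment) contains four statements that bear on this point.

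- The general rule is: "All subjects, investigators, and study personnel involved in the conduct of the study, including data management, will be blinded to study drug treatment assignment". The only exception is a prespecified statistician or programmer who has access to the randomization code.
- If the investigator breaks the code without being able to discuss it beforehand, "he/she must notify the medical monitor immediately of the blind breaking incident without revealing the subject's treatment assignment".
- The closing paragraph states: "If treatment assignment is unblinded for an individual subject, study personnel will be notified of that subject's treatment assignment". The sentence goes on to say that the other subjects' assignments stay concealed, and the section concludes that the overall blind is preserved.
- On what follows for the subject: "If a subject's treatment assignment is unblinded, he/she may or may not be asked to withdraw from the study". The investigator decides after consulting the medical monitor.

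Protocol 10.2.2.4 says who makes the dermal ratings. For irritation, "All subjects will be evaluated by a trained investigator or designee using the Berger and Bowman scale"; at clinic visits, "patch adhesion will be assessed by the investigator or a designee". Discomfort and adhesive residue are likewise assessed by the investigator or a designee.

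SAP 3.5 allows individual unblinding only in a medical emergency and adds a general principle that it should not harm the integrity of the study. It does not say who may be told.

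**The concern.** The notification sentence uses the same term, study personnel, as the rule on who must stay blinded, and it sets no limit by role or need. Followed as written, it passes the assignment beyond whoever opened the code. Because the subject may continue, those staff can go on rating that subject with the arm known.

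The dermal ratings are partly matters of observer opinion, such as barely perceptible against definite erythema. Irritation, discomfort, adhesion and residue together form a named secondary objective (Protocol 6.2). They are where a rater's knowledge of the arm could most plausibly affect the data.

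**Working it through.** The point concerns wording, and the plan gives no figure to reproduce. The check is to set the statements side by side.

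**1. Are the statements in 9.5 compatible?** The general rule keeps study personnel, including data management, blinded. The closing paragraph tells study personnel the arm of an unblinded subject. It names no subset, and the continuation of the sentence restricts which subjects are unblinded but not which staff are informed. For the subject concerned, the two statements pull in opposite directions unless study personnel means something narrower in the second, and 9.5 does not say so.

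**2. Does the reporting rule settle it?** It binds the investigator towards the medical monitor, when prior discussion was not possible. It does not mention anyone else. It does show that containing the assignment was the intent even for a senior recipient, which makes the unrestricted notification harder to explain.

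**3. Is the notification limited to emergencies?** No. Protocol 9.5 also provides for non-emergency code breaks after discussion with the medical monitor, whereas SAP 3.5 permits emergencies only. The notification sentence covers any individual unblinding.

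**4. Can affected data still be collected?** Yes, because withdrawal is optional. The same section also asks, for any broken code, for the date and reason for study discontinuation, which fits poorly with optional withdrawal. These statements should be reconciled. This point takes no position on whether the subject should stay.

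**5. Who gains knowledge only because of this sentence?** The investigator may already know, having been allowed to break the code. Those newly informed would be designee raters, other site staff and, on the broad reading, data management.

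**6. Size.** The documents give no expected number of code breaks, so assume 0 to 3 among about 300 subjects. SAP 8.5.1 counts subjects by worst adhesion score, and SAP 8.5.2 counts subjects with a combined irritation score of 3 or more. Using the planned arm sizes (75, 75 and 150) as approximate denominators:

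- one subject reclassified in an active arm: 1/75 = 1.3 percentage points
- one subject reclassified in placebo: 1/150 = 0.7 percentage points
- upper end, all three in one active arm and all reclassified: 3/75 = 4.0 percentage points
- lower end, no code breaks: 0

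The upper end requires every assumed break to fall in one arm, every such subject to stay, and every rating to cross the threshold because the arm was known.

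**The case against.** The best reply is that the sentence can be read narrowly. It promises that opening one code leaves the others closed. In the earliest of the protocol versions supplied, the section also says that study personnel use the IVRS for emergency unblinding, so the people notified may simply be those who requested the code. That reading is possible, but the IVRS statement is absent from the current 9.5, which leaves the term unrestricted.

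Other text narrows the exposure. Protocol 11.2.4 directs withdrawal when treatment of an adverse event departs from the protocol. The SAE report items in 11.2.6.1 ask whether and when the investigator was unblinded, and do not list the arm. These provisions reduce the number of subjects who stay after unblinding, or limit disclosure by one route. They do not limit what site staff are told.

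A reader might infer more than the documents support:

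- **A direct contradiction of the reporting rule.** That rule concerns one sender, one recipient and one circumstance, so it and the notification sentence can both be obeyed. The conflict is with the general blinding rule.
- **Bias in the primary endpoint.** WOMAC pain is the subject's own rating, PGA and PGIC are self-administered, and 9.5 does not say the subject is told. Staff administer WOMAC, so influence is conceivable but indirect. Even an assumed 4-point shift on the 20-point scale in one subject moves a 75-subject mean by 4/75 = 0.05 points.
- **Biased causality assessments.** Under Protocol 11.2.2.5, "The investigator must make an assessment of each AE's relationship to study drug". An investigator who has broken the code knows the arm whether or not the sentence exists, so most of this argument falls away.

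**Conclusion.** The point stands as a minor but real flaw in wording. Protocol 9.5 states a rule that widens an individual unblinding, against its own requirement that study personnel remain blinded, and it allows the subject to go on being assessed.

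The consequence is limited to subjects whose code is broken and mainly to dermal ratings made by staff other than the person who opened the code. At roughly 1.3 percentage points per reclassified subject in an active arm, under an assumed 0 to 3 code breaks, it would not be expected to change the trial's efficacy conclusion.

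The documents do not support presenting this as a threat to the primary analysis or as a gap that the SAP must fill. A subject who continues on the assigned patch still fits the primary estimand in SAP 7.1, and a sensitivity run on so few subjects would tell the reader almost nothing.

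**What to change.** Reconcile the statements in Protocol 9.5 by replacing the notification sentence. The replacement should say that:

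- study personnel are told only that a code break occurred for the subject
- the assignment is disclosed only to those who need it to manage the emergency, and to pharmacovigilance where required
- other site raters, data management and the sponsor study team stay blinded.

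The replacement should apply to every individual code break. Protocol 9.5 and SAP 3.5 should also be aligned on whether non-emergency breaks are allowed.

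The cost is a change of protocol wording. Emergency care loses nothing, because the investigator can still break the code. No SAP sensitivity analysis is needed. Protocol 9.5 already has the date and reason for unblinding recorded on the eCRF, so affected subjects can be identified in the study report if any occur.

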9.6. Selection of Doses and Administration in the Study

The dose of diclofenac [REDACTED] in a patch size of [REDACTED] applied [REDACTED] and rotated between [REDACTED] on the knee (inner and outer knee) is based on the following considerations:

- [REDACTED]
- [REDACTED]
- Dose that targets diclofenac exposure after HP-5000 patch application that is similar to that of registered topical diclofenac products and considerably lower than that of oral diclofenac tablets.
- The data from previous studies investigating irritation and PK support the proposed dose of [REDACTED] and a patch size of [REDACTED] applied [REDACTED] and rotated between [REDACTED] on the knee for the lead formulations (HP-5000 [REDACTED] and HP-5000 [REDACTED]).

9.7. Dose Adjustment Criteria

Dose adjustment is NOT allowed in this study.

9.8. Drug Accountability

The investigator (or pharmacist, as appropriate) must maintain adequate records of the receipt and conditions of all study drugs, dispensing, return, or other disposition of study drug including the date, quantity dispensed to each subject, batch or code number, identification of subjects (subject number [and initials]) who received study drug and any reasons for departure from the

protocol-dispensing regimen. Receipt of study drug must also be confirmed within IVRS. The drug accountability records, along with used and unused packaging must be available for monitoring, auditing, or inspection. Each site must keep accurate records of drug received at site, dispensed to the subjects.

The investigator will not supply study drug to any person except those named as sub-investigators (on the Form FDA 1572), designated study personnel, and subjects in this study. The investigator will not dispense study drug from any study sites to other than those listed (on the Form FDA 1572).

Study drug may not be relabeled or reassigned for use by other subjects. If any of study drugs is not dispensed, lost, stolen, unusable, or is received in a damaged container, this information must be documented and reported to Noven and appropriate regulatory agencies, as required.

At the completion of the study, a final reconciliation of all study drugs (used and unused) must be performed by the site and only unused patches must be returned to the sponsor (or designated location). The unused study drug must be left in the original packaging and returned to the sponsor (or designee) for destruction.

9.9. Treatment Compliance

Treatment compliance with study drug regimens will be assessed by study personnel via the counts of returned unused patches, patch application, removal and by questioning the subject, if necessary, at every post-randomization visit. Treatment compliance will also be calculated as the number of patches applied divided by the prescribed number of patches over a given period, expressed as a percentage.

At Visits 3 through 5 or any Early Termination Visit, the study drug (patches) from the previous Double-blind Treatment Phase will be returned to the investigator. The study drug will be inventoried and noncompliance defined assuming less than 80% or more than 120% of study drug during any evaluation period (visit to visit). If the subject is noncompliant, the Medical Advisor should be contacted to discuss the subject's eligibility to continue in the study.

The subject must be counseled if compliance is not satisfactory (used 6 or less patches per week). If a subject has been noncompliant on two consecutive visits, the subject may be withdrawn early from the study for non-compliance.

For each 28-day study drug administration period, subjects will be asked to record their daily intake/use of rescue medication/study drug in the eDiary. Deviations from the planned doses (overdose, missed dose or timing) will be recorded on the subjects' eCRF. These eDiaries will be reviewed by study personnel at each study visit and will be collected as source documents. Information from that subject eDiary will be transcribed on the appropriate eCRF pages for documentation of subject compliance with study drug. Compliance will include the following:

- 1. Telephone Follow-up:** A telephone follow-up call will be performed between Screening (Visit 1) and Baseline (Visit 2), before the start of the Washout Period and another one during the Follow-up Period.
- 2. Patient Education:** At all clinical study visits, the investigator will explain the importance of the following:
 - a. applying study medication [REDACTED] to the target knee after showering/bathing;
 - b. recording patient eDiary information every day;
 - c. accurately reporting pain;
 - d. accurately reporting rescue medication use;
 - e. understanding when to return for next visit and the importance of returning on schedule; and
 - f. adhering to the overall research plan.

During Screening (Visit 1), the investigator will provide the subject with an introduction to the various questionnaires including the [REDACTED] that will be used during the entire study and the patient eDiary.

- 3. Patient eDiary :** The subject eDiary will be used by the subject to record required assessments including the time of patch application/removal, the NRS scores, the use of rescue medication, and questionnaires about adhesion, skin irritation, discomfort and adhesive residue.
- 4. Rescue Medication:** If needed, subjects will be allowed to take up to a maximum of 2 grams (4 tablets) of oral acetaminophen per day as rescue medication for pain of the target and/or the non-target knee except within 2 calendar days prior to Baseline Visit (V2) and within 1 calendar day for all subsequent visits (V3, V4 and V5). Information

regarding the use of rescue medication, such as the number of tablets, will be recorded on the appropriate concomitant medication eCRF.

